**Statement of Compliance**

This study will be conducted in accordance with the Code of Federal Regulations on the Protection of Human Subjects (45 CFR Part 46), 21 CFR Parts 50, 56, 312, and 812 as applicable, any other applicable US government research regulations, and institutional research policies and procedures. The International Conference on Harmonisation (“ICH”) Guideline for Good Clinical Practice (“GCP”) (sometimes referred to as “ICH-GCP” or “E6”) will be applied only to the extent that it is compatible with FDA and DHHS regulations. The Principal Investigator will assure that no deviation from, or changes to the protocol will take place without documented approval from the Institutional Review Board (IRB), except where necessary to eliminate an immediate hazard(s) to the trial participants. All personnel involved in the conduct of this study have completed Human Subjects Protection Training.

## List of Abbreviations

AE	Adverse Event/Adverse Experience
CFR	Code of Federal Regulations
CRF	Case Report Form
DCSU	Department of Dermatology Clinical Trials Unit
EIS	Electrical Impedance Spectroscopy (EIS)
GCP	Good Clinical Practice
HIPAA	Health Insurance Portability and Accountability Act
ICF	Informed Consent Form
ICH	International Conference on Harmonisation
IRB	Institutional Review Board
MOP	Manual of Procedures
NYU	New York University
NYULMC	New York University Langone Medical Center
NIH	National Institutes of Health
PI	Principal Investigator
QA	Quality Assurance
QC	Quality Control
SAE	Serious Adverse Event/Serious Adverse Experience
SOP	Standard Operating Procedure
US	United States

**Protocol Summary**

[figure not shown]
Title	SpotCheck: Comparison of enhanced telemedicine versus in-person evaluation for the diagnosis of skin cancer
Brief Summary	The aim of this pilot is to test a novel, telemedicine-based skin cancer diagnostic platform (SpotCheck) that has the potential to improve access to needed dermatologic care for those living in medically underserved areas. In this study we will recruit participants with 1-3 skin lesions concerning for skin cancer. Each concerning lesion will be evaluated by an enhanced telemedicine method using clinical images, a dermoscopic image, and a measurement by Nevisense, a low-cost skin cancer diagnostic device currently FDA-cleared for use in dermatologists' offices. Each subject will also be evaluated in-person by a clinical dermatologist with dermoscopy so the accuracy of the telemedicine diagnosis can be compared to the current gold standard. This pilot project will assess both diagnostic congruence and patient-centered outcomes regarding this service, which will provide preliminary data for larger follow up studies, including those in medically underserved areas.
Phase	Pilot Proof of Concept Study
Objectives	Aim 1: Determine the agreement between in-person and teledermatologist evaluations of concerning skin lesions identified by participants in a walk-in clinic setting Aim 2: Determine the degree to which the enhanced telemedicine method addresses patient needs and preferences (i.e. patient-centered outcomes)
Methodology	Prospective single arm study of a diagnostic intervention against the gold standard dermatological care, singly blinded to diagnosticians.
Endpoint	Primary endpoint: Congruency between biopsy recommendation of enhanced telemedicine evaluation and in-person dermatology evaluation Secondary endpoints: 1) Specificity, sensitivity, false-positive rate, false-negative rate, positive predictive value, and negative predictive value of enhanced telemedicine evaluation and in-person evaluation to diagnose skin cancer; 2) Participant satisfaction of intervention in addressing patient centered outcomes
Study Duration	Study is estimated to be open for 24 months or longer to be sufficiently powered
Participant Duration	Estimated duration is one to four weeks subject to participant's findings
Duration of IP administration	Clinical and dermoscopic image acquisition for teledermatologist evaluation will take <2 minutes per lesions, and Nevisense data acquisition will take <2 minutes per lesion
Population	At least 18 years of age Females and Males
Study Sites	NYU School of Medicine The Ronald O. Perelman Department of Dermatology Ambulatory Care Center Dermatology Clinical Trials Unit [name]
Number of participants	650 enrolled participants
Description of Study Agent/Procedure	Telemedicine evaluation using combined dermoscopic imaging with DermLite Cam (3Gen) and/or Barco Demetra and electrical impedance spectroscopy using Nevisense 3.0
Reference Therapy	In-person dermatologist evaluation

CONFIDENTIAL

[figure not shown]
Key Procedures	Clinical and dermoscopic imaging of skin lesions, Nevisense measurement of skin lesion electrical impedance. Possible skin biopsy for lesion(s) identified as concerning for malignancy
Statistical Analysis	Percent agreement of biopsy recommendation in diagnostic intervention compared to control. For biopsied lesions, sensitivity and specificity of in-person dermatologist and teledermatologist evaluation for skin cancer diagnosis will also be determined. Success by patient centered outcomes will be analyzed by questionnaires using Likert scales.

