### **2.4.2 Known Potential Benefits**

Study subjects will have up to three lesions of concern screened by a dermatologist for skin cancer at no cost. We anticipate participation in the study to offer immediate and long-term psychological benefit for subjects who have benign lesions and who receive reassurance. We estimate ~90% of subjects will have lesions not requiring biopsy and will receive such reassurance. Of the remaining subjects, it is likely that 8% will undergo a biopsy and receive a benign diagnosis, which will also be reassuring.

For subjects who are found to have malignant diagnoses (~2%), we anticipate substantial long-term physical, psychological, and economic benefit from this free screening service. These subjects would benefit from earlier detection of a malignancy that otherwise may have gone un-diagnosed. Inevitably the potential for early detection of melanoma or other skin cancers is associated with less costly treatment and less complicated care, decreased morbidity and mortality and overall improved outcomes.

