## **7 Study Procedures and Schedule**

### **7.1 Study Procedures/Evaluations**

#### **7.1.1 Study Specific Procedures**

- Assessment of eligibility (number of lesions, location of lesions)
- Informed Consent
- Enrollment questionnaire (Supplement K)
- Nevisense EIS measurement
- Imaging of the lesion(s) of concern using the DermLite Cam and stored on MoleCam software and MoleCam drive behind NYU MCIT firewall OR using the Barco Demetra and stored on its associated cloud server
- Imaging of the lesion(s) of concern uploaded to EPIC EMR research note using study specific camera or EPIC HAIKU
- Numbering of skin lesions using Devon Skin Marker to verify same lesion evaluated across all assessments
- Administration of part 1 of study completion questionnaire (Supplement L)
- Skin lesion examination by in-person dermatologist
- Phone call to communicate telemedicine recommendation within 3 business days (phone script as Supplement M & N)
- Skin biopsy, if recommended by either the in-person dermatologist or the telemedicine evaluation
  - A skin biopsy is a small procedure that removes a sample of skin from the surface of the body. The method utilized will be either a shave or punch technique. The maximum size of a punch biopsy will be 6mm and these wounds are generally closed with absorbable sutures and do not require a return visit for suture removal. A skin biopsy takes <15 minutes including preparation time, administration of intradermal anesthesia using lidocaine 1% with epinephrine 1:100,000, removal of the skin sample, achievement of hemostasis, dressing the wound, and providing instructions for home care. Samples will be placed in formalin for routine processing.
- Administration of final study completion questionnaire (Supplement L).

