### 10.2 Analysis Datasets

All eligible lesions evaluated by both the teledermatologists and the in-person dermatologist.

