### 10.3 Description of Statistical Methods

#### 10.3.1 General Approach

The general approach will be to determine the agreement between in-person recommendation and the telemedicine (tele) recommendation. For this reason the data will be categorical in nature and the specific measures to be assessed are described below. We will also examine the performance characteristics of the tele approach (e.g. sensitivity, specificity, etc.) using the in-person dermatologist biopsy decision as the 'gold standard'(primary endpoint). However, it is possible that with respect to the pathology results (secondary endpoint), the tele approach may have a higher sensitivity and specificity to diagnose skin cancer than the in-person dermatologist. For this reason, we will also examine the performance of the tele and in-person biopsy decisions against the pathology results as the 'gold standard'.

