#### 10.3.2 Analysis of the Primary Efficacy Endpoint(s)

To determine the agreement between in-person recommendation and the telemedicine (tele) recommendation we can calculate the number of discordant benign vs. malignant diagnoses; specifically, the number of subjects that were recommended a biopsy from the in-person dermatologist but were recommended no biopsy from the teledermatology team, and the number of subjects that were recommended no biopsy from the in-person dermatologist but biopsy by the teledermatologist team. We can calculate the Kappa coefficient as a measure of the degree of concordance or agreement with confidence intervals. We can also calculate "sensitivity" and "specificity" of the tele method assuming in-person diagnosis as the gold standard. Similarly, we can separately evaluate the agreement between in-person and: 1) dermoscopy alone; and 2) Nevisense (EIS score  $\geq 4$ ) without dermoscopy. We will also estimate the improvement (if any) of using both methods compared to one method. We expect the Kappa coefficient to be close to one, and high "sensitivity" and "specificity" (close to 1) for the SpotCheck method assuming in-person diagnosis as the gold standard.

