#### 10.3.3 Analysis of the Secondary Endpoint(s)

Secondary endpoint (1) will be a descriptive analysis of Sensitivity, Specificity, Positive Predictive Value, and Negative Predictive Value, using the histopathology results as the gold standard. We will assess potential difference or advantages in terms of: a) enhanced telemedicine diagnostic system; b) telemedicine Nevisense alone; c) telemedicine clinical + dermoscopy alone; and d) in-person dermatologist diagnosis. Sensitivity, Specificity, Positive Predictive Value, and Negative Predictive Value will be reported with an upper and lower confidence interval. Lesions with missing data will not be included in the relevant analyses (see Study Design schematic footnote 3). Participants lost to follow-up for reporting his/her biopsy results will be included in the analysis as the data required for analysis has been collected.

As another secondary endpoint, we will be evaluating the enhanced telemedicine service's impact on patient centered outcomes. Descriptive statistics for this secondary endpoint (2) (patient questionnaires, Supplement L will be presented as percentages. Study completion questionnaires may be qualitatively analyzed for themes and quantified by thematic representation across participants. Participant agreement of thematic categories will be calculated as percentages as a summary measure. Factors for stratification may include participants with a biopsy procedure and those without biopsy procedure as well as diagnosis of malignancy or benign lesion within those with biopsy. Participants with missing study completion questionnaire results due to inadequate duration of phone call will not be included.

As a final secondary endpoint (3), we will estimate the number of lesions that may benefit from the additional information of the Nevisense score to the clinical and dermoscopic exam. This estimation will be provided by the in-person dermatologist, and separately by each of the three teledermatologists (Supplement T & U). The estimates will be expressed as percentages. Any lesion with missing data in the in-person dermatologist and teledermatologist plan will not be included in analysis. Participants lost to follow-up will still be included in analysis of this endpoint as required data for this endpoint determination has been captured in the first visit.

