**10.4 Sample Size**

Number of subjects to recruit and screen is estimated to be 650 or fewer. Number of participants eligible is estimated to be 500 or fewer. Based on the previously mentioned Norwegian study, we anticipate a biopsy recommendation rate of 10% between the telemedicine and in-person evaluations. With each participant presenting with 1-3 lesions, an estimate of 1000 evaluated lesions (2 per participant on average) is possible. Assuming a biopsy recommendation 10% from this historical data, there will be likely 50 - 100 biopsies recommended and 450 - 900 lesions not recommended for biopsy.

We anticipate 2% of the sample will be lost to follow up based on historical data. Missing data is estimated at 4% based on those lost to follow up and technical error based on historical data. We anticipate 1% of participants to withdraw based on historical data. Participants who have formally withdrawn from the study will not be included in primary or secondary endpoint analysis, nor will they be included in the analysis datasets.

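### Computed on biopsied lesions only, specificity of the telemedicine and in-person evaluations collapses by construction, NPV is unreliable, and sensitivity is relative to cancers found by either evaluation

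*Combined protocol and SAP*

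**What the plan says.** Secondary endpoint 1 is diagnostic accuracy for skin cancer. The Statistical Analysis entry of the Protocol Summary sets the denominator: "For biopsied lesions, sensitivity and specificity of in-person dermatologist and teledermatologist evaluation for skin cancer diagnosis will also be determined". Section 10.3.3 describes the analysis as "Sensitivity, Specificity, Positive Predictive Value, and Negative Predictive Value, using the histopathology results as the gold standard", with confidence intervals, for the full telemedicine system, Nevisense alone, imaging alone and the in-person dermatologist. Section 10.3.1 makes clear that the tests judged against pathology are the two biopsy decisions.

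Histology is obtained under one rule, in Section 7.1.1: "Skin biopsy, if recommended by either the in-person dermatologist or the telemedicine evaluation". Section 7.3 confirms that a lesion judged not suspicious by both evaluations is not biopsied. Participation lasts one to four weeks (Section 5.5), and no later reference result is planned for unbiopsied lesions.

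Section 10.2 gives the analysis set as "All eligible lesions evaluated by both the teledermatologists and the in-person dermatologist". It does not say what disease status an unbiopsied lesion takes. Section 10.3.3 drops lesions with missing data, but it refers to footnote 3 of the study schematic, which concerns lesions without a Nevisense score or dermoscopic image, not lesions without histology.

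**The concern.** The same two decisions define the test results and decide which lesions enter the denominator. Lesions negative on both evaluations hold nearly all the true negatives, and restricting to biopsied lesions removes every one of them. On the plan's own expectation, "there will be likely 50 - 100 biopsies recommended and 450 - 900 lesions not recommended for biopsy", that is about 90% of the data.

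The study intends to comment on absolute accuracy. Section 10.3.1 raises the possibility that "the tele approach may have a higher sensitivity and specificity to diagnose skin cancer than the in-person dermatologist", and Section 2.1 hopes for performance comparable to or better than in-person examination. Under the biopsied-only calculation, the better the two evaluations agree, the lower both reported specificities become. Section 10.3.2 says: "We expect the Kappa coefficient to be close to one". The false-positive rate, also listed as an endpoint in the Summary, would approach 100%. Read on their own, these figures would say that neither evaluation has any useful specificity, and they would pass in that form to the larger studies this pilot is meant to inform.

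**Working it through.** **The plan's own counts.** Section 10.4 applies a 10% biopsy recommendation rate. 500 lesions give 50 biopsied and 450 not; 1000 give 100 and 900. Both ends reproduce the stated ranges.

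**The bound, which needs no assumed rates.** Among benign lesions, let *a* be flagged by both evaluations, *b* by telemedicine only, *c* by in-person only and *d* by neither. Biopsy removes *d*.

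- Biopsied-only specificity: telemedicine *c*/(*a*+*b*+*c*); in-person *b*/(*a*+*b*+*c*).
- Their sum is (*b*+*c*)/(*a*+*b*+*c*), which is at most 1, so at least one is 50% or lower.
- As agreement becomes perfect, *b* and *c* go to 0 and so do both specificities.
- All-lesion telemedicine specificity is (*c*+*d*)/(*a*+*b*+*c*+*d*), never below the biopsied-only value.

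**Size for specificity.** Section 2.4.2 expects about 2% of subjects to have a malignancy, and says of benign biopsies: "Of the remaining subjects, it is likely that 8% will undergo a biopsy and receive a benign diagnosis". Applying both per lesion is an assumption. With 1000 lesions it gives 20 cancers, 80 benign biopsied and 900 unbiopsied, here taken as benign. FP is the number of the 80 that telemedicine flags.

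| FP | Biopsied only, (80 − FP)/80 | All lesions, (980 − FP)/980 |
|---|---|---|
| 40 | 50% | 95.9% |
| 60 | 25% | 93.9% |
| 72 | 10% | 92.7% |
| 80 (perfect agreement) | 0% | 91.8% |

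Other inputs at perfect agreement:

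- The 500-lesion end (40 benign biopsied, 450 unbiopsied) gives 0% against 450/490 = 91.8%.
- With 10 cancers (2% of 500 subjects, one each), 0/90 against 900/990 = 90.9%.
- With the 29:1 benign-to-malignant ratio of Section 14.3, 100 biopsies hold 100/30 = 3.3 cancers and 96.7 benign lesions: 0% against 900/996.7 = 90.3%.

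If *m* = 9 of the 900 unbiopsied lesions (1%, assumed) are in fact cancers, the FP = 60 row becomes (920 − 9)/(980 − 9) = 911/971 = 93.8%, so the all-lesion figure hardly depends on this.

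**Sensitivity.** Assume telemedicine flags 18 of the 20 cancers found. Reported: 18/20 = 90.0%. True: 18/(20 + *m*), which is 90.0% at *m* = 0 and 18/29 = 62.1% at *m* = 9. If every recommended biopsy is done, the reported value equals the true one, or exceeds it when both evaluations miss any cancer.

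**NPV (FP = 60).**

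- 18 of 20 found: reported 20/22 = 90.9%; all-lesion (922 − 2 − *m*)/922 = 99.8% to 98.8%. Too low.
- All 20 found: reported 20/20 = 100%; all-lesion (920 − *m*)/920 = 100% to 99.0%. Equal or too high.
- Perfect agreement: no biopsied lesion is test-negative, so NPV is undefined.

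**Recommended biopsies without a result.** In-person biopsies can be done at Visit 1 (Section 7.3.2). Telemedicine-only ones need a return visit (Section 7.3.3), so losses may be uneven. Assume benign lesions split 40 both, 20 telemedicine-only, 20 in-person-only, and cancers 17, 2, 1. Complete data give a false-positive ratio of 60/60 = 1.00 and a true-positive ratio of 19/18 = 1.06. Now lose 4 telemedicine-only biopsies (Section 10.4's 4% missing, applied to 100 biopsies and all placed here). If all 4 are benign, the ratios are 56/60 = 0.93 and 1.06. If 2 are cancers, they are 58/60 = 0.97 and 17/18 = 0.94.

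**The case against.** The restriction to biopsied lesions appears only in the Summary; Sections 4.2.2 and 10.3.3 do not repeat it, and Section 10.2 takes in all lesions seen by both evaluations. That is fair, but it does not rescue the plan. Section 10.2 gives unbiopsied lesions no disease status, and a 2×2 table against histology cannot be filled without one. The Summary is the only place that names the denominator.

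The comparison between evaluations largely survives. If telemedicine flags 80 of the 80 benign biopsied lesions and in-person 40, the false-positive ratio is 2.0 on either denominator (80/80 over 40/80, or 80/980 over 40/980). This stands: absolute levels and absolute differences are distorted, not which evaluation is better. PPV is likewise unbiased when all recommended biopsies are done.

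Perfect agreement is an extreme. Telemedicine is positive if any one reader is (Section 6.1.4), so telemedicine-only flags are likely and the two specificities may be unequal. The bound on their sum still holds.

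The sensitivity direction needs complete biopsies. With 16 cancers flagged by both, 2 by telemedicine only and 2 by in-person only, 50% uptake of telemedicine-only biopsies gives 17/19 = 89.5% against a true 90.0%. The exception is real but small. Access to outside records (Sections 7.3.2 and 7.3.3) and forfeited payment (Section 15.3) also limit lost histology.

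Finally, this is a descriptive pilot with no hypothesis tests (Section 10.1), and the all-lesion agreement results will be reported alongside. That limits the consequences; it does not make the specificity estimate right.

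**Conclusion.** The concern holds. Followed as the Summary states, secondary endpoint 1 would report specificities of roughly 0% to 50% for telemedicine where the all-lesion values are about 92% to 96%. The bound is arithmetic and rests only on the either-positive biopsy rule. The percentages also rest on applying the 8% and 2% subject rates to lesions and on the assumed overlap between evaluations; changing the cancer count or adding a few missed cancers barely moves specificity. The sensitivity and NPV figures depend more heavily on assumed detection and missed-cancer counts and show direction and scale only. Nevisense-alone and imaging-alone metrics are also only partly verified, with uncertain direction of bias: Nevisense specificity could be too high, because its false positives on common benign lesions (Section 2.1) may never be biopsied. The primary agreement endpoint is not affected.

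**What to change.** Reconcile the Summary, Section 10.2 and Section 10.3.3 on the denominator and on the status of unbiopsied lesions. For telemedicine and in-person evaluation, specify:

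1. PPV, cancers found per 1000 lesions, and benign biopsies per cancer.
2. Paired ratios of true-positive and of false-positive rates, telemedicine to in-person, among either-positive lesions with histology, with confidence intervals that allow for several lesions per participant. Report recommended biopsies without a result, split into both, telemedicine-only and in-person-only, with a sensitivity analysis setting them all benign, then all malignant.
3. Specificity and NPV over all evaluated lesions, first counting lesions negative on both as non-cancer, then over a stated range of missed cancers (for example 0 to 1% of them, labelled as an assumption).
4. Sensitivity labelled as relative to cancers found by either evaluation.
5. Nevisense-alone and imaging-alone metrics labelled as conditional on biopsy, with uncertain direction of bias.

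The cost is SAP wording and a little more analysis; no extra biopsies or data are needed. The price is that absolute sensitivity is no longer claimed, and all-lesion specificity and NPV rest on a stated assumption.
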